9.3. Patient Withdrawal Criteria

For all patients, it is the intent that patients who discontinue study medication (at any time) for any reason but do not withdraw consent will continue to be followed for all protocol-planned study visits through the completion of the 24-week treatment period, and will have all endpoints (including efficacy) collected accordingly.

The Investigator, Sponsor, or its designee may decide a patient should discontinue treatment at any time and for any reason. In addition, patients will discontinue randomized treatment if they:

- Experience an intolerable adverse event: such events include, but are not limited to, adverse event ≥ Grade 4*, bone marrow-related events, a ≥ Grade 3* cardiac event (*CTCAE v5.0 criteria);
- Require a medication that is prohibited by the protocol. However, under certain circumstances, and in consultation with the Medical Monitor, short-term use of a prohibited medication may not necessitate withdrawal of treatment when its use is unlikely to unfavorably alter the risk-benefit of subject participation;
- In the opinion of the Investigator, have any medically appropriate reason;
- Become pregnant;
- Have a serious adverse event associated with a SARS-CoV-2 infection;
- The Investigator believes that further treatment is undesirable or the risk-benefit profile has become unfavorable.

Furthermore, dose interruptions lasting more than 21 days may require treatment discontinuation on a case by case basis following consultation with the Medical Monitor.

In addition, patients are free to withdraw from participation in the study at any time, for any reason, and without prejudice. The Investigator must withdraw any patient from the study if the patient withdraws consent and requests to stop participating in the study.

Patients who withdraw or are withdrawn from the study will not be replaced.

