10.2.1. Dose Interruption Safety Criteria and Management

Patients who experience hematologic adverse events as described in Table 3, significant clinical laboratory abnormality, or adverse events that may reflect an unfavorable risk-benefit profile may have their dose interrupted at the discretion of the Investigator. The Medical Monitor should be consulted whenever possible prior to decisions for dose interruption.

Patients who withdraw consent and therefore are discontinued from the study should undergo an Early Termination Visit and subsequent Safety Follow-up Visit as appropriate per Section 9.3.1 Patient Withdrawal Procedures, and associated adverse events followed as described in Section 12 Adverse Events.

Hematology parameters will be assessed bi-weekly for the first 4 weeks of the Treatment Period, and every 4 weeks thereafter for the remainder of the study. Prior to dose interruption, hematology parameters should be confirmed with repeat testing at an Unscheduled Visit within 72 hours, except in severe cases (i.e.: neutrophil counts below 0.5 x 10⁹/L) where immediate interruption of dosing is necessary for the safety of the patient. Blood draws confirming dose interruption criteria should occur prior to the first daily dose on the day of draw.

Dose interruption requirements for hematologic abnormalities are provided below. However, less significant changes may warrant clinical intervention and the Investigator should use his/her best clinical judgment when considering a dose interruption whether for singular or aggregate

hematology results above the limits provided in Table 3, or for other clinical signs, symptoms, or considerations that suggest dose interruption is in the best interest of the patient.

Table 3: Selected Hematologic Thresholds for Dose Interruption

Neutrophil Count	Dose Adjustment
Between 0.5 to 1 x 10 ⁹ /L	Interrupt dose until recovered to greater than 1.5 x 10 ⁹ /L and
(Grade 3)	resume dosing at previous dose
Less than 0.5 x 10 ⁹ /L (Grade 4)	Severe case: Interrupt dose immediately and repeat CBC with differential within 72 hours. Recommend hematology consult and contact medical monitor. Permanent discontinuation of treatment should occur upon repeat confirmation of value
Female Hemoglobin Level	Dose Adjustment
Less than 10 g/dL	Interrupt dose until recovered to greater than 10.5 g/dL and resume dosing at previous dose
Male Hemoglobin Level	Dose Adjustment

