Less than 11.5 g/dL	Interrupt dose until recovered to greater than 12 g/dL and resume dosing at previous dose
Platelet Count	Dose Adjustment
Less than 75 x 10 ⁹ /L	Interrupt dose until recovered to greater than 100 x 10 ⁹ /L and resume dosing at previous dose
Greater than 750 x 10 ⁹ /L	Interrupt dose until recovered to less than 600 x 10 ⁹ /L and resume dosing as prescribed by the Investigator

Upon dose interruption, the parameters that triggered the interruption should be monitored at least weekly until either: 1) recovery above the threshold for dosing resumption is achieved, or 2) a 21-day dose interruption period has elapsed, at which time a discussion between the PI and the Medical Monitor should occur to evaluate whether or not the subject should discontinue treatment permanently. In the case of severe neutropenia (neutrophil counts less than 0.5 x $10^9/L$) patient should interrupt dose **immediately** and repeat CBC with differential within 72 hours. The Medical Monitor should be contacted and a hematology consult should be made if appropriate. Permanent discontinuation of treatment should occur upon repeat confirmation of value. Patients who discontinue treatment due to lack of acceptable recovery of parameters should continue to be followed for all safety and efficacy assessments through the completion of the 24-week treatment period, and will have all endpoints (including efficacy) collected accordingly.

Subjects with both a positive SARS-CoV-2 test (antigen or antibody) AND signs or symptoms consistent with SARS-CoV-2 infection should immediately interrupt dosing with study drug. Dose interruption should continue until symptoms subside (it is not necessary to have a negative SARS-CoV-2 test result). If symptoms do not subside within a 21-day dose interruption period, a discussion between the PI and the Medical Monitor should occur to evaluate whether or not the subject should discontinue treatment permanently. Signs and symptoms include, but are not limited to: fever or chills, cough, shortness of breath or difficulty breathing, fatigue, muscle or body aches, headache, new loss of taste or smell, sore throat, congestion or runny nose, nausea or

vomiting, diarrhea, trouble breathing, persistent pain or pressure in the chest, new confusion, inability to wake or stay awake, bluish lips or face.

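### Section 9.3 requires a permanent stop for a Grade 4 adverse event, but Table 3 restarts drug after any low platelet count, and no text ranks the two rules

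*Protocol*

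**What the plan says.** Section 9.3 of the protocol lists conditions under which patients must come off randomized treatment. The first is an intolerable adverse event, explained as follows: "such events include, but are not limited to, adverse event ≥ Grade 4*, bone marrow-related events, a ≥ Grade 3* cardiac event". The grades are CTCAE v5.0.

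Table 3 in Section 10.2.1 gives the action for each abnormal count:

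- Platelets below 75 x 10^9/L: "Interrupt dose until recovered to greater than 100 x" 10^9/L, then restart at the earlier dose.
- Hemoglobin below 10 g/dL in women: "Interrupt dose until recovered to greater than 10.5 g/dL and resume dosing at previous dose".
- Hemoglobin below 11.5 g/dL in men: "Interrupt dose until recovered to greater than 12 g/dL and resume dosing at previous dose".
- Neutrophils below 0.5 x 10^9/L, labelled Grade 4: "Severe case: Interrupt dose immediately and repeat CBC with differential within 72 hours", and later "Permanent discontinuation of treatment should occur upon repeat confirmation of value".

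After an interruption, the parameter is followed until "recovery above the threshold for dosing resumption is achieved" or until 21 days have passed, when the investigator and Medical Monitor discuss whether to stop. Section 10.2 leaves the choice between interrupting and discontinuing for intolerability to the Investigator, consulting the Medical Monitor. Section 8.1 says in general terms that severity decides how cytopenias are handled.

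**The concern.** The same patient can fall under both instructions. After a Grade 4 platelet event, a site working from Table 3 would put the patient back on the earlier dose once the count passed 100 x 10^9/L. A site working from Section 9.3 would not. With about 25 sites, no data monitoring committee (SAP Section 12) and no prospective stopping criteria for the study (Protocol Section 9.5), the patient-level rules carry the safety burden and should give one answer.

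Reporting is affected too. The same event would be counted among those leading to discontinuation (Tables 14.3.1.4.x) or among those leading to interruption (Tables 14.3.1.5.x), depending on which section the site followed.

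**Working it through.** The plan states no figure on this point, so the check compares the texts.

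**Step 1. Does a low count reach Section 9.3?** Section 9.3 acts on adverse events. Section 12.1 makes a laboratory abnormality an adverse event when it is judged clinically important enough to need dose interruption, and uses thrombocytopenia as its example of a term to record. Section 12.2.2 grades all events by CTCAE v5.0. A platelet count that leads to interruption can therefore become a graded adverse event, and at Grade 4 the mandatory stop applies.

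**Step 2. Does Table 3 cover the same event?** The low-platelet row starts at 75 x 10^9/L and has no floor, so it covers every lower value. No numeric Grade 4 cut-off is needed to see the overlap.

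**Step 3. Compare the three low-count cell lines.**

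| Cell line | Table 3 action at the lowest values | Against Section 9.3 at Grade 4 |
|---|---|---|
| Platelets | Interrupt, restart on recovery | Direct conflict |
| Hemoglobin | Interrupt, restart on recovery | Conflict only if an anemia event is graded 4 |
| Neutrophils | Interrupt at once, stop for good if confirmed | Differs: 9.3 has no confirmation step |

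One of the three lines has a permanent-stop tier, and 3 - 1 = 2 have none. CTCAE grades are printed on the 2 neutrophil rows and on no hemoglobin or platelet row.

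**Step 4. Why platelets and hemoglobin are not equal.** Neither document gives a Grade 4 cut-off for either. SAP Section 9.5 grades laboratory results on the number alone where CTCAE includes them, and it names platelets among the graded parameters. It does not name hemoglobin in that context, so the documents do not show that a low hemoglobin value alone can be Grade 4.

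**Step 5. Look for text that sets the order.**

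- Section 10.2 allows either interruption or discontinuation by judgement and sends the reader to 10.2.1, not to 9.3. That does not match a mandatory stop.
- Section 10.2.1 cites 9.3.1 only for patients who withdraw consent. It does not cite the discontinuation criteria in 9.3.
- The 21-day review depends on duration, not grade.
- Section 8.1 gives no cut-offs and no precedence.

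Nothing in either document ranks Section 9.3 against Table 3.

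**The case against.** The best defence is that the texts fit together. Section 9.3 is categorical, Table 3 concerns interruptions, and a patient already discontinued has no interruption to resume from. This is the sensible reading and the one to adopt, but it is not written. Table 3 states a permanent stop where one is meant (neutrophils) and Investigator discretion over resumption where that is meant (platelets above 750 x 10^9/L). A site could fairly take the silence in the low-platelet row as deliberate.

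The second defence is oversight. Section 10.2 requires consultation on whether to interrupt or discontinue, and Section 9.3 also requires a stop when the Investigator finds the risk-benefit balance unfavorable. This stands as real mitigation, and it would be wrong to infer that sites decide alone. It does not close the gap. Section 10.2.1 is softer ("The Medical Monitor should be consulted whenever possible prior to decisions for dose interruption"), and no text ties the contact to the decision to restart when a count recovers before 21 days.

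A reader might also infer three stronger claims that the documents do not support:

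- That every very low hemoglobin value triggers the conflict. Step 4 shows why it does not.
- That the bone marrow wording in 9.3 overrides all of Table 3. The term is ungraded and undefined. Read that widely, it would leave the low-count restart rows with no use, including the one for Grade 3 neutropenia.
- That interruption at the Table 3 limits is merely optional. The section opens with permissive wording, but then calls these limits requirements and reserves clinical judgement for lesser changes.

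**Conclusion.** The point holds. For a Grade 4 thrombocytopenia event, Section 9.3 requires a permanent stop and Table 3 directs a restart. For an anemia event the conflict depends on the event being graded 4. For neutrophils the mismatch is narrower and concerns only whether the value must be confirmed first.

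This assumes that a thrombocytopenia adverse event can be graded 4 under CTCAE v5.0. That is consistent with Protocol Section 12.2.2 and SAP Section 9.5, but the tables themselves are not in the documents.

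The documents give no rate of Grade 4 cytopenia, so the number of patients affected cannot be estimated. Frequency should be low: screening excludes platelets below 100 x 10^9/L, scheduled counts run throughout, and interruption begins at 75 x 10^9/L. Nor should a reader infer a threat to the efficacy results. Patients who stop drug without withdrawing consent are still followed for all endpoints under Section 9.3. This is a patient-safety and consistency correction that should be made, not a flaw in the trial's analysis.

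**What to change.** Make three changes together:

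1. In Section 10.2.1, state that resumption under Table 3 applies only when no discontinuation criterion in Section 9.3 has been met.
2. In Section 9.3, state that for a Grade 4 hematologic laboratory value drug is interrupted immediately and discontinued permanently once a repeat within 72 hours confirms the value. This brings 9.3 and the neutrophil tier into agreement. Adding confirm-first tiers to Table 3 while leaving 9.3 unchanged would recreate the mismatch for an unconfirmed value.
3. In Section 9.3, state that the bone marrow wording does not include the counts below Grade 4 that Table 3 manages by interruption.

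The cost is a short amendment or clarification letter. No patients or scheduled visits are added, because Section 10.2.1 already provides for a repeat count within 72 hours. Two effects should be acknowledged. For a Grade 4 platelet value the repeat would follow interruption rather than precede it. A single Grade 4 laboratory value that is not confirmed would no longer end treatment under 9.3. Grade 4 events that do not rest on a laboratory value stay under the existing mandatory stop.

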9.3.1. Patient Withdrawal Procedures

If a patient withdraws consent from further participation in the study, the Investigator will record the reason(s) for early termination on the relevant electronic case report form (eCRF). The specific reason for the withdrawal should be carefully documented on the eCRF.

9.4. Emergency Unblinding of Treatment Assignment

In the case of a medical requirement to break the blind to determine appropriate treatment for an adverse event, unblinding of a patient's treatment assignment can be achieved through the study-specific Interactive Web Response System. If possible, the Investigator should discuss the circumstances with the Medical Monitor(s) prior to accessing unblinding information. In the event of a blind break, the Medical Monitor(s) will be notified through the electronic data capture system. The patient for whom the blind is broken should be subsequently withdrawn

Concert Pharmaceuticals, Inc.

from the study. The details regarding the process of breaking the blind are outlined in the Medical Monitoring Plan and the Pharmacy Manual.

9.5. Criteria for Study Termination

There are no prospective stopping criteria for this study. The Sponsor reserves the right to discontinue the study at any time for clinical or administrative reasons.

Any termination required by the Sponsor must be implemented by the Investigator, if instructed to do so, in a time frame that is compatible with the patient's well-being.

10. DESCRIPTION OF STUDY TREATMENTS

10.1. Description of Treatments

Part A

Period 1. Patients will be stratified by extent of scalp hair loss with approximately 170 patients initially randomized to the 8 mg BID CTP-543 dose and approximately 130 patients initially randomized to the 12 mg BID CTP-543 dose.

Period 2. Eligible patients for Period 2 will be to randomized to a lower dose or placebo in a 1:1 ratio. Specifically, patients previously on 8 mg BID will be randomized to 4 mg BID or placebo. Patients previously on 12 mg BID will be randomized to 8 mg BID or placebo.

Part B

Eligible patients for Part B will be assigned to the dose they previously took in Part A, Period 1. Consequently, patients will receive either 8 mg BID or 12 mg BID for the remainder of their participation in the study.

For all study phase, patients will take the first dose of study drug in the clinic on Day 1 of the Treatment Period and will be instructed to take study drug approximately every 12 hours (\pm 3 hours) without regard to food for the duration of the study Phases.

10.2. Dose-Adjustment Criteria

No individualized dose adjustment is allowed during any part of the study except in the event of intolerability, for which a dose interruption or patient discontinuation may occur at the judgement of the Investigator in consultation with the Medical Monitor (see Section 10.2.1 below for details).

10.2.1. Dose Interruption Safety Criteria and Management

Patients who experience hematologic adverse events as described in Table 3, significant clinical laboratory abnormality, or adverse events that may reflect an unfavorable risk-benefit profile may have their dose interrupted at the discretion of the Investigator. The Medical Monitor should be consulted whenever possible prior to decisions for dose interruption.

Patients who withdraw consent and therefore are discontinued from the study should undergo an Early Termination Visit and subsequent Safety Follow-up Visit as appropriate per Section 9.3.1 Patient Withdrawal Procedures, and associated adverse events followed as described in Section 12 Adverse Events.

Hematology parameters will be assessed bi-weekly for the first 4 weeks of the Treatment Period, and every 4 weeks thereafter for the remainder of the study. Prior to dose interruption, hematology parameters should be confirmed with repeat testing at an Unscheduled Visit within 72 hours, except in severe cases (i.e.: neutrophil counts below 0.5 x 10⁹/L) where immediate interruption of dosing is necessary for the safety of the patient. Blood draws confirming dose interruption criteria should occur prior to the first daily dose on the day of draw.

Dose interruption requirements for hematologic abnormalities are provided below. However, less significant changes may warrant clinical intervention and the Investigator should use his/her best clinical judgment when considering a dose interruption whether for singular or aggregate

hematology results above the limits provided in Table 3, or for other clinical signs, symptoms, or considerations that suggest dose interruption is in the best interest of the patient.

Table 3: Selected Hematologic Thresholds for Dose Interruption

Neutrophil Count	Dose Adjustment
Between 0.5 to 1 x 10 ⁹ /L	Interrupt dose until recovered to greater than 1.5 x 10 ⁹ /L and
(Grade 3)	resume dosing at previous dose
Less than 0.5 x 10 ⁹ /L (Grade 4)	Severe case: Interrupt dose immediately and repeat CBC with differential within 72 hours. Recommend hematology consult and contact medical monitor. Permanent discontinuation of treatment should occur upon repeat confirmation of value
Female Hemoglobin Level	Dose Adjustment
Less than 10 g/dL	Interrupt dose until recovered to greater than 10.5 g/dL and resume dosing at previous dose
Male Hemoglobin Level	Dose Adjustment
Less than 11.5 g/dL	Interrupt dose until recovered to greater than 12 g/dL and resume dosing at previous dose
Platelet Count	Dose Adjustment
Less than 75 x 10 ⁹ /L	Interrupt dose until recovered to greater than 100 x 10 ⁹ /L and resume dosing at previous dose
Greater than 750 x 10 ⁹ /L	Interrupt dose until recovered to less than 600 x 10 ⁹ /L and resume dosing as prescribed by the Investigator

Upon dose interruption, the parameters that triggered the interruption should be monitored at least weekly until either: 1) recovery above the threshold for dosing resumption is achieved, or 2) a 21-day dose interruption period has elapsed, at which time a discussion between the PI and the Medical Monitor should occur to evaluate whether or not the subject should discontinue treatment permanently. In the case of severe neutropenia (neutrophil counts less than 0.5 x $10^9/L$) patient should interrupt dose **immediately** and repeat CBC with differential within 72 hours. The Medical Monitor should be contacted and a hematology consult should be made if appropriate. Permanent discontinuation of treatment should occur upon repeat confirmation of value. Patients who discontinue treatment due to lack of acceptable recovery of parameters should continue to be followed for all safety and efficacy assessments through the completion of the 24-week treatment period, and will have all endpoints (including efficacy) collected accordingly.

Subjects with both a positive SARS-CoV-2 test (antigen or antibody) AND signs or symptoms consistent with SARS-CoV-2 infection should immediately interrupt dosing with study drug. Dose interruption should continue until symptoms subside (it is not necessary to have a negative SARS-CoV-2 test result). If symptoms do not subside within a 21-day dose interruption period, a discussion between the PI and the Medical Monitor should occur to evaluate whether or not the subject should discontinue treatment permanently. Signs and symptoms include, but are not limited to: fever or chills, cough, shortness of breath or difficulty breathing, fatigue, muscle or body aches, headache, new loss of taste or smell, sore throat, congestion or runny nose, nausea or

vomiting, diarrhea, trouble breathing, persistent pain or pressure in the chest, new confusion, inability to wake or stay awake, bluish lips or face.

Subjects who have signs or symptoms consistent with SARS-CoV-2 infection should be tested for SARS-CoV-2 and do not have to dose interrupt unless the test result is positive. Subjects who have a positive SARS-CoV-2 test (antigen or antibody) but do not have any signs or symptoms consistent with SARS-CoV-2 infection are not required to dose interrupt.

Table 4: SARS-CoV-2 Dose Interruption Criteria

SARS-CoV-2 Test Result	SARS-CoV-2 Symptoms	Dose Interruption
Positive	Yes	Yes
Positive	No	No
Negative	Yes	No

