Patient safety will be monitored throughout the trial by the Investigator and supported by regular review by the Medical Monitor. The subject will be tested to ensure they do not have the Hepatitis B or C virus, thyroid function abnormalities or latent or active Tuberculosis, during the screening period for Part A. Chemistry and hematology laboratory values will be assessed under fasted conditions bi-weekly for the first month of the treatment period (Part A, Period 1 and Part B), followed by every 4 weeks through the remainder of the study (all Parts). Lipid levels will be assessed every 4 weeks throughout the study. In light of the COVID-19 pandemic, challenges in the conduct of study visits may arise from quarantines, site closures, and/or travel limitations. To ensure the safety of trial participants and to minimize risk to trial integrity, alternative methods for drug dispensation and assessments, including telemedicine visits and clinical laboratory blood draws at a local laboratory or via a Home Health Care agency, may be offered for those trial participants who may no longer have access to the investigational site. Significant cytopenias or other hematologic abnormalities will be managed by severity through dose interruption or discontinuation, and signs and symptoms of infection will be closely monitored and treated promptly. Patients who experience intolerable symptoms during treatment may discontinue treatment at the judgement of the Investigator, but will continue in the study and complete all assessments unless they withdraw consent. Patients may withdraw consent at any time.

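### Protocol Section 10.2.1 contradicts itself on whether dose interruption is required or discretionary when a Table 3 hematologic limit is met

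*Protocol*

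**What the plan says.** Protocol Section 10.2.1 gives the dose-interruption rules in several places.

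- **Paragraph 1** lists three triggers: the hematologic events in Table 3, other significant laboratory abnormalities, and adverse events suggesting an unfavorable risk-benefit balance. For all three it says that patients "may have their dose interrupted at the discretion of the Investigator", and it asks for the Medical Monitor to be consulted beforehand where possible.
- **Paragraph 3** asks for a repeat test within 72 hours before interrupting. It exempts severe cases such as neutrophils below 0.5 x 10^9/L, where "immediate interruption of dosing is necessary for the safety of the patient".
- **Paragraph 4** opens with "Dose interruption requirements for hematologic abnormalities are provided below". It then asks the investigator to use clinical judgement for less marked changes.
- **Table 3** has six rows: neutrophils 0.5 to 1 and below 0.5 x 10^9/L, female hemoglobin below 10 g/dL, male hemoglobin below 11.5 g/dL, and platelets below 75 and above 750 x 10^9/L. Each row tells the site to interrupt. The male hemoglobin row, for example, reads "Interrupt dose until recovered to greater than 12 g/dL and resume dosing at previous dose".

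**The concern.** The same laboratory value falls under two rules of different force. Under paragraph 1, continuing to dose at a Table 3 value is a permitted choice. Under paragraph 4 and the table, it breaches a requirement.

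The values at issue are not marginal. Each Table 3 limit lies beyond the matching exclusion limit in Protocol Section 9.2: neutrophils 1.5 x 10^9/L, hemoglobin 10.5 g/dL (female) or 12.0 g/dL (male), and platelets 100 or 600 x 10^9/L. A patient at a Table 3 value could not have entered the study. Protocol Section 9.5 sets no prospective stopping criteria and SAP Section 12 plans no data monitoring committee, so patient-level rules carry more of the protection.

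There is also a reporting side. SAP Section 7.1 defines a deviation as noncompliance with the protocol, so the same conduct could be recorded as a deviation or not. SAP Sections 9.2 and 9.3 tabulate drug interruptions and the adverse events leading to them. If sites read the rule differently, those counts would partly reflect the reading.

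**Working it through.** There is no figure to reproduce. The check is a comparison of texts.

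1. **Do the two rules cover the same events?** Yes. Paragraph 1 does not merely reserve general discretion; it points to Table 3 by name. Paragraph 4 introduces Table 3 itself. Both cover every row.

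2. **Do they differ in force?** Yes. Paragraph 1 is permissive. Paragraph 4 speaks of requirements, and all six rows are imperative. The repeat test in paragraph 3 confirms the value; it does not make interruption optional once the value is confirmed. In the high-platelet row the investigator is named, but only for restarting: "resume dosing as prescribed by the Investigator".

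3. **Does any text say which prevails?** None in the two documents. The precedence statements that do exist, in SAP Sections 2 and 4, concern analyses and reporting conventions. Protocol Section 10.2 speaks of investigator judgement for intolerability and defers to 10.2.1, so it neither settles the point nor adds a second conflict.

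4. **Is any row settled separately?** Neutrophils below 0.5 x 10^9/L are. Paragraph 3 calls immediate interruption necessary, and the text after the table repeats it.

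5. **What was probably meant?** Mandatory interruption. Protocol Section 8.1 says "Significant cytopenias or other hematologic abnormalities will be managed by severity through dose interruption or discontinuation". SAP Section 9.5 draws the values on box plots as dose interruption limits.

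6. **Could the section have been clearer?** Its own SARS-CoV-2 text shows how. Patients with symptoms and a positive test are told to interrupt, those positive without symptoms are told that they need not, and Table 4 gives a yes or no for each listed combination.

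7. **A consequence in one case.** Take a man whose hemoglobin is below 11.5 g/dL, confirmed on repeat, and whose investigator continues dosing. Paragraph 1 makes this compliant. Paragraph 4 and the row make it a deviation. The sponsor's review under SAP Section 7.1 grades deviations as minor or major but does not decide which paragraph applies.

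8. **A related slip.** Paragraph 4 extends judgement to "hematology results above the limits provided in Table 3". For the five lower limits this means results that have not reached the limit. For platelets above 750 x 10^9/L, an upper limit, it literally describes the results at which the row says to interrupt.

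**The case against.** The strongest reply is that paragraph 4 already allocates discretion. It states requirements and then turns to lesser changes, which places judgement on values that do not reach a limit. Paragraph 1 can be read as a general permission for three broad triggers, with the rule for one of them set out below it. An investigator who kept dosing would have to pass over paragraph 4, the row, and the consultation with the Medical Monitor that Section 10.2 and paragraph 1 of 10.2.1 both ask for. Section 11.10 adds central laboratory processing, investigator sign-off of each report, and discussion of clinically significant hematologic abnormalities with the Medical Monitor. Section 9.3 lists "bone marrow-related events" among the intolerable events that lead to discontinuation.

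Most of this stands. It makes the mandatory reading the likely one and the practical risk modest. It does not remove the conflict. Paragraph 1 places Table 3 events under discretion expressly, and consultation does not make interruption required. The bone-marrow term in Section 9.3 is not defined. The Medical Monitoring Plan and the monitoring plan may say how Table 3 is applied, but they are not available here, so the absence of a precedence rule is established only for the Protocol and SAP.

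A reader might go on to infer that the protocol leaves most Table 3 rows without a mandatory rule, because only the lowest neutrophil row has its own extra text. That does not follow. The requirements sentence in paragraph 4 is mandatory text outside the table and covers every row, so a count of rows would measure only how often the instruction is repeated.

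**Conclusion.** The inconsistency is real and concerns a safety rule. It is a drafting conflict and not a questionable design choice. Two incompatible instructions apply to the same events; the intent is probably mandatory, but neither document says so. The conclusion rests on the wording of the Protocol and SAP alone.

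Its size in patients cannot be given, because neither document states how often Table 3 values occur. A reader might infer that patients will in fact be kept on drug at these values, or that the efficacy results are biased. The documents support neither: the likely reading and the safeguards point the other way, and nothing in the conflict alters an endpoint, the sample size or an analysis method. The correction is still worth making, because the rule protects patients taking a JAK inhibitor and the remedy is small.

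**What to change.** Make three changes to Protocol Section 10.2.1:

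- In paragraph 1, delete the reference to Table 3 hematologic events from the discretionary sentence.
- Add a sentence saying that interruption is required when a Table 3 limit is met and confirmed by repeat testing, that it is immediate and does not wait for confirmation when neutrophils are below 0.5 x 10^9/L, and that it is otherwise at the investigator's discretion.
- In paragraph 4, replace the phrase about results above the limits with wording for results not meeting a Table 3 limit, so that it also works for platelets above 750 x 10^9/L.

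A short cross-reference in Section 10.2 is optional. Protocol Section 14.4 requires a permanent change to go through an amendment, so this belongs in the next one. The cost is two reworded sentences and one new one, with no new data, visits or analyses.
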